7.8.2 Prohibited Medications

Use of the following products during the study is prohibited: alcohol, cannabis, illicit drugs, any known 5-HT_{2A} receptor antagonist or inverse agonist, any strong cytochrome P450 3A4 inhibitor or cytochrome P450 3A4 inducer, or any drugs with known psychotropic properties or any non-psychotropic drugs with potential central nervous system effects.

Any positive result on urine drug screen should be discussed with the Sponsor or designee.

7.8.3 Rescue Medications

Medications for the acute treatment of extrapyramidal symptoms and akathisia are allowed.

Zolpidem may be taken for insomnia, in the evening at bedtime and prior to midnight for the treatment of insomnia. If zolpidem is not available in specific regions, another sedative hypnotic may be approved by the Sponsor or designee.

The date of each dose of rescue medication administration as well as the name and dosage regimen of the rescue medication must be recorded on the eCRF.

7.9 Treatment after Discontinuation

Patients whose depressive symptoms worsen or are determined by the Investigator not to be adequately controlled prior to completing the Open-label Treatment Period may, at the Investigator's discretion, be discontinued from the Open-label Treatment Period in order to start appropriate treatment. This new treatment will not be provided by the Sponsor. Patients who initiate a new treatment for depression during the study must be discontinued from the study and should also return for the Safety Follow-up visit.

All patients who prematurely discontinue from the Open-label Treatment Period regardless of cause should be seen for a final assessment at the ET Visit. All patients who prematurely discontinue from the Open-label Treatment Period should return for the Safety Follow-up visit.

8. EFFECTIVENESS, SAFETY, AND OTHER ASSESSMENTS

8.1 Effectiveness Assessments

8.1.1 Montgomery-Asberg Depression Rating Scale (MADRS)

The MADRS is a 10-item scale designed to measure the overall severity of depressive symptoms (Montgomery and Åsberg, 1979). Individual items are rated by the Investigator or Sponsor-approved rater on a scale of 0 to 6 in which a score of 6 represents the most severe symptoms for each item assessed. Patients are rated on items assessing feelings of sadness, lassitude, pessimism, inner tension, suicidality, reduced sleep or appetite, difficulty in concentration, and lack of interest. The MADRS total score ranges from 0 to 60. The MADRS will be completed by a Sponsor-approved rater.

8.1.2 Clinical Global Impression-Severity

The Clinical Global Impression Scale-Severity provides the clinician's assessment of the overall severity of the patients psychopathology (Guy, 1976). The CGI-S asks the clinician: "Considering your total clinical experience with this particular population, how mentally ill is the patient at this time?" which is rated on the following seven-point scale: 1=normal, not at all ill; 2=borderline mentally ill; 3=mildly ill; 4=moderately ill; 5=markedly ill; 6=severely ill; 7=among the most extremely ill patients.

The CGI-S will be completed by a trained and Sponsor-approved rater.

8.2 Safety

All patients who receive study drug (ie, lumateperone 42 mg) will be evaluated for safety. Safety assessments will include incidence of AEs, C-SSRS assessment for suicidality, EPS assessment as measured by AIMS, BARS, and SAS scales, clinical laboratory evaluations, ECG evaluations, vital sign measurements, and physical examination and neurological findings. Additional details pertaining to safety assessments are provided in the Schedule of Evaluations (Table 1-1).

8.2.1 Adverse Events

8.2.1.1 Definition of Adverse Event

An AE is any untoward medical occurrence associated with the use of a drug in humans, whether or not considered drug-related. An AE can therefore be any unfavorable and unintended sign (including an abnormal laboratory finding, for example), symptom, or disease temporally associated with the use of a medicinal product, whether or not considered related to the medicinal product (ICH-E2A; 21 CFR 312.32[a]).

NOTE: Medical procedures scheduled prior to obtaining informed consent but occurring during the study and for a pre-existing condition which did not worsen should not be captured as AEs but the medical reason for the procedure should be listed in the medical history if related to a pre-existing condition.

8.2.1.2 Definition of Serious Adverse Event

An SAE is any untoward medical occurrence that at any dose:

- Results in death
- Is life threatening

NOTE: An AE is considered "life-threatening" if, in the view of either the Investigator or Sponsor, its occurrence places the patient at immediate risk of death. It does not include an AE that, had it occurred in a more severe form, might have caused death.

- Requires inpatient hospitalization or prolongation of existing hospitalization
- Results in persistent or significant disability/incapacity, or
- Is a congenital anomaly/birth defect

Important medical events that may not result in death, be life threatening, or require hospitalization may be considered serious when, based on appropriate medical judgment, they may jeopardize the patient and may require medical or surgical intervention to prevent one of the outcomes listed in this definition. Examples of such medical events include allergic bronchospasm requiring intensive treatment in an emergency room or at home, blood dyscrasias or convulsions that do not result in patient hospitalization, or the development of study drug dependency or drug abuse.

Emergency room visits that do not result in hospitalization should be evaluated for one of the other serious outcomes to determine whether they qualify as SAEs.

8.2.1.3 Classification of Adverse Events and Serious Adverse Events

8.2.1.3.1 Severity

The Investigator will provide an assessment of the severity of each AE by recording a severity rating on the appropriate AE reporting page of the patient's eCRF. *Severity*, which is a description of the intensity of manifestation of the AE, is distinct from *seriousness*, which implies a patient outcome or AE-required treatment measure associated with a threat to life or functionality (Section 8.2.1.2).

Severity will be assessed according to the following scale:

Mild: A type of AE that is usually transient and may require only minimal treatment or

therapeutic intervention. The event does not generally interfere with usual activities

of daily living.

Moderate: A type of AE that is usually alleviated with additional specific therapeutic

intervention. The event interferes with usual activities of daily living, causing discomfort but poses no significant or permanent risk of harm to the research

patient.

Severe: A type of AE that interrupts usual activities of daily living, or significantly affects

clinical status, or may require intensive therapeutic intervention.

8.2.1.3.2 Causality Assessment

For each reported AE and SAE, the Investigator must provide an assessment of causal relationship to study drug. Causal relationship must be assessed by answering the following question:

Is there a reasonable possibility study drug caused the event?

Yes: There is evidence to suggest a causal relationship between study drug and adverse event, ie:

- There is a reasonable temporal relationship between study drug and the event, and/or
- The event is unlikely to be attributed to underlying/concurrent disease, other investigational products, or other factors, and/or
- Positive dechallenge and/or rechallenge exist

OR

No: There is no evidence to suggest a causal relationship between study drug and adverse event, ie:

- There is no reasonable temporal relationship between study drug and the event, or
- The patient did not take study drug, or
- The event is likely to be attributed to underlying/concurrent disease, other investigational products, or other factors.

There may be situations in which an SAE has occurred and the Investigator has minimal information to include in the initial report to the Sponsor. However, it is important that the Investigator always makes an assessment of causality for every event before the initial transmission of the SAE data to the Sponsor. The Investigator may change his/her opinion of causality in light of follow-up information and send an SAE follow-up report with the updated causality assessment.

For each AE/SAE, the Investigator must document in the medical notes that he/she has reviewed the AE/SAE and has provided an assessment of causality. The causality assessment must be recorded on the appropriate AE reporting page of the patient's eCRF.

8.2.1.4 Time Period and Frequency of AE and SAE Reporting

The Investigator will report all AEs from the time informed consent was obtained until the final protocol-defined study visit or last known dose date of study drug + 1 day, whichever is later.

The Investigator will report all SAEs from the time informed consent was obtained until 30 days after the last known dose date of study drug.

At each visit, patients are to be queried regarding any AEs that have occurred since the previous visit. Patients will be asked to volunteer information with a nonleading question such as, "How do

you feel since your last visit?"

8.2.1.5 Adverse Event Reporting Procedures

8.2.1.5.1 Reporting Adverse Events

All AEs, including overdose with sequelae or intentional overdose of study drug or other medication, must be recorded on the appropriate AE reporting page of the patient's eCRF whether or not they are considered causally related to study drug.

For every AE, the Investigator must:

- Provide an assessment of the seriousness of the event (ie, is it an SAE?), as well as the severity and casual relationship. See Section 8.2.1.2 for the definition of SAEs and Section 8.2.1.5.2 for SAE reporting procedures.
- Document all actions taken with regard to study drug.
- Detail any other treatment measures taken for the AE.

Any AEs that are ongoing at the time of the final protocol-defined study visit will be followed until the condition returns to pre-study status, has resolved or stabilized, or can be explained as being unrelated to study drug. If a follow-up visit is deemed necessary for appropriate safety surveillance, it will take place within 30 days of the final protocol-defined study visit.

8.2.1.5.2 Reporting Serious Adverse Events

The Sponsor is required to inform worldwide regulatory authorities of SAEs that meet specific criteria. Therefore, the Sponsor must be notified immediately regarding any SAE that occurs after informed consent is obtained. Within 24 hours of learning of any AE that meets one of the criteria for an SAE, study center personnel must report the event to the Sponsor on the SAE Form. In addition to completing the SAE form, the Study Physician may also be notified by telephone.

If, during follow-up, any nonserious AE worsens and eventually meets any SAE criterion, that AE should be recorded as a new SAE.

Preplanned hospitalizations (eg, elective procedures for pre-existing conditions that did not worsen, such as cosmetic surgery and hysterectomy) are excluded from SAE reporting.

The study center must email or fax the SAE form to the SAE email address below. Even if an initial report is made by telephone, the SAE form containing all available details must still be emailed or faxed within 24 hours of knowledge of the event at the study center.

Supplemental information should be submitted as soon as available and may include laboratory results, radiology reports, progress notes, hospital admission and emergency room notes, holding and observation notes, discharge summaries, autopsy reports, and death certificates.

The Investigator is expected to take all therapeutic measures necessary for resolution of the SAE. Any medications or procedures necessary for treatment of the SAE must be recorded on the appropriate pages of the patient's eCRF. All SAEs will be followed until resolution or stabilization. The Sponsor may contact the study center to solicit additional information or follow up on the event.

8.2.2 Potential Hy's Law Cases

Study center personnel must report every patient who meets potential Hy's Law criteria from the time the ICF is signed until 30 days after the final protocol-defined study visit or the last known dose of study drug (if the final visit does not occur).

The criteria for potential Hy's law cases are as follows:

ALT or AST \geq 3 × ULN and

Total bilirubin $\geq 2 \times ULN$ and

Alkaline phosphatase $< 2 \times ULN$

Study center personnel must report every subject who meets these potential criteria. Typically, these analytes will be obtained from the same sample, but they may come from multiple samples taken within a 24-hour period. This requirement applies from the time the ICF is signed for the study until 30 days after the last known dose of study drug.

A laboratory alert for potential Hy's Laws cases will be in place, and the laboratory must notify Investigators and the Sponsor immediately when the above criteria have been met. The Sponsor must be notified of any potential Hy's Law case as soon as possible (within 24 hours of learning of a potential Hy's Law case). Refer to the SAE reporting procedures (Section 8.2.1.5.2) even if no AE has occurred.

Every effort to determine the cause of the liver enzyme abnormalities must be made, and close monitoring should be initiated in conjunction with the Study Physician and in accordance with the FDA Guidance for Industry: Drug Induced Liver Injury—Pre-Marketing Clinical Evaluation (July 2009).

8.2.3 Pregnancy

Female patients will not be eligible for inclusion in the study if they have a positive pregnancy test at the Screening/Baseline Visit (Visit 1/Day 1). Any patient who becomes pregnant during the Open-label Treatment Period must be discontinued from the study.

Study center personnel must report every pregnancy, including pregnancies in female partners of male study patients, from the time consent was obtained until the final protocol-defined study visit or last known dose of study drug (if a final visit does not occur).

Within 24 hours of learning of the pregnancy, study center personnel must report the event to the Sponsor on the Pregnancy Notification Form and email or fax it to the email address or fax number below even if no AE has occurred.

While pregnancy itself is not considered to be an AE or SAE, any pregnancy complication or elective termination of a pregnancy for medical reasons will be reported as an AE or SAE. If the pregnancy is associated with an SAE (eg, spontaneous miscarriage or if the mother is hospitalized for hemorrhage), a separate SAE form must be filed as described in Section 8.2.1.5.2 with the appropriate serious criterion (eg, hospitalization) indicated in addition to the Pregnancy Notification/Outcome Form.

Abnormal pregnancy outcomes (eg, spontaneous abortion, fetal death, stillbirth, congenital anomalies, ectopic pregnancy) are considered SAEs and will be reported as such.

Any pregnancy in a study patient or in a female partner of a male study patient must be followed to term/termination. The outcome, including status of the mother and the child, must be reported to the Sponsor by completing a follow-up Pregnancy Outcome Form.

8.2.4 **Clinical Laboratory Determinations**

Blood and urine samples for clinical laboratory tests will be collected as specified in the Schedule of Evaluations (Table 1-1). Because the Screening/Baseline Visit (Visit 1) is the same visit as Visit 8/Day 43 of the lead-in study, laboratory assessments performed at Visit 8/Day 43 of the lead-in study are considered to be the Screening/Baseline laboratory assessments for this openlabel study. Patients are required to fast for at least 10 hours before the collection of clinical laboratory blood tests at designated visits.

Laboratory results should be reviewed by the Investigator/sub-investigator throughout the study. Any abnormal laboratory results judged to be clinically significant should be discussed with the Sponsor or its designee. For safety reasons or at the discretion of the Investigator, repeat laboratory assessments may be performed at an unscheduled visit.

The following clinical laboratory levels will be measured:

- Hematology: hematocrit; hemoglobin; red blood cell count with indices (mean corpuscular volume, mean corpuscular hemoglobin, and mean corpuscular hemoglobin concentration); reticulocytes; white blood cell count and differential (neutrophils, lymphocytes, monocytes, eosinophils, and basophils) reported as percent (%) and absolute values; and platelet count.
- Chemistry: albumin; alkaline phosphatase; ALT; AST; bilirubin (total, direct); blood urea nitrogen; calcium; chloride; cholesterol (high-density lipoprotein [HDL] and low-density lipoprotein [LDL] will be calculated and reported); creatinine; creatine phosphokinase; gamma-glutamyl transferase; glucose; insulin; lactate dehydrogenase; phosphate; potassium; prolactin; sodium; triglycerides; total protein; uric acid. HbA1c and TSH (reflex

free T3 and T4) will be measured at the Screening/Baseline Visit (Visit 1/Day 1) and Visit 16/ET only.

- **Urinalysis**: macroscopic (pH, specific gravity, glucose, protein, ketones, bilirubin, nitrates, blood) and microscopic (red blood cells/high-power field, white blood cells/high-power field, casts, epithelial cells, crystals, granulation).
- Urine Drug Screen (UDS): Urine testing for drugs (eg, amphetamines, barbiturates, benzodiazepines, cannabinoids, cocaine metabolites, methadone, opiates, phencyclidine) will be performed.
- Urine and serum pregnancy tests: Female patients who are of childbearing potential (FOCBP) will undergo a serum and a urine pregnancy test at Screening/Baseline Visit (Visit 1/Day 1). For all other visits, a urine pregnancy test will be performed. Unscheduled pregnancy tests may be administered at any time during the study at the Investigator's discretion.

A central laboratory will be used to evaluate all urine and blood samples, which will be collected, processed, and stored according to the instructions provided in the Laboratory Manual. Additional information regarding sample shipment is provided in the Laboratory Manual.

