1. PROTOCOL SYNOPSIS AND SCHEDULE OF EVALUATIONS

CLINICAL STUDY SYNOPSIS:	Study ITI-007-503
Title of Study	An Open-label, Multicenter Trial to Assess the Safety and Tolerability of Lumateperone as Adjunctive Therapy in the Treatment of Patients with Major Depressive Disorder
Study Centers (Country)	Approximately 120 study centers (US and Non-US)
Development Phase	Phase 3
Objectives	Primary Objective To evaluate the safety and tolerability of lumateperone 42 mg administered orally once daily for approximately 26 weeks as adjunctive treatment to antidepressant therapy (ADT) in patients with major depressive disorder (MDD). Secondary Objectives To evaluate whether lumateperone 42 mg administered orally once daily for approximately 26 weeks as adjunctive treatment to ADT improves or maintains improvement of depressive symptoms in patients with MDD as measured by change from baseline in the Montgomery-Åsberg Depression Rating Scale (MADRS) total score and in the Clinical Global Impression Scale-Severity (CGI-S) score.
Study Design	This is an international, multicenter, open-label, fixed dose, 26-week study of patients with MDD. Eligible patients from the lead-in studies will enter the Open-label Safety Study at the Screening/Baseline Visit (Visit 1/Day 1), at which point patient eligibility will be assessed and informed consent obtained. At the Screening/Baseline Visit (Visit 1/Day 1), which is the same visit as Visit 8/Day 43 of the lead-in study, eligible patients will receive open-label lumateperone 42 mg once daily for approximately 26 weeks. Patients will continue their background ADT from the lead-in study. Patients will be seen for weekly visits through Visit 5/Week 4. Thereafter, visits will occur every two weeks. A Safety Follow-up visit will occur on Visit 17/Day 197, approximately 2 weeks after the last dose of open-label lumateperone 42 mg.
Number of Patients	Approximately 760 patients are planned to be enrolled in the Open-label Safety Study. No de novo patients will be enrolled.

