Study Week	0	1 (+/-3 days)	2 (+/-3 days)	3 (+/-3 days)	4 (+/-3 days)	6 (+/3 days)	8 (+/-3 days)	10 (+/-3 days)	12 (+/-3 days)	14 (+/-3 days)	16 (+/-3 days)	18 (+/-3 days)	20 (+/-3 days)	22 (+/-3 days)	24 (+/-3 days)	26 (+/-3 days)	28 (+/-3 days)
Informed consent	X																
Inclusion/Exclusion criteria	X																
Physical examination	X															X	
Vital signs³	X	X	X	X	X	X	X	X	X	X	X	X	X	X	X	X	X
12-lead ECG ⁴	X	X					X				X					X	
Clinical laboratory assessments (hematology, serum chemistry, urinalysis) ⁵	X	X					X				X					X	
Urine drug testing ⁶	X	X					X				X					X	
Serum/urine pregnancy test ⁷	X	X			X		X		X		X		X		X	X	
MADRS	X	X	X	X	X		X		X		X		X		X	X	X
CGI-S	X	X	X	X	X		X		X		X		X		X	X	
AIMS/BARS/SAS	X	X			X		X		X		X		X		X	X	
C-SSRS	X	X	X	X	X	X	X	X	X	X	X	X	X	X	X	X	X
PK sampling		X8					X9										
AEs/SAEs	X	X	X	X	X	X	X	X	X	X	X	X	X	X	X	X	X
Concomitant medications	X	X	X	X	X	X	X	X	X	X	X	X	X	X	X	X	X
ADT prescription dispensation ¹⁰	X																
ADT compliance check	X	X	X	X	X	X	X	X	X	X	X	X	X	X	X	X	

Study Period	Screening /Baseline Visit ¹		Open-label Treatment Period ² Fo											Safety Follow Up			
Visit Number	1	2	3	4	5	6	7	8	9	10	11	12	13	14	15	16/ET	17
Study Day	1	8	15	22	29	43	57	71	85	99	113	127	141	155	169	183	197
Study Week	0	1 (+/-3 days)	2 (+/-3 days)	3 (+/-3 days)	4 (+/-3 days)	6 (+/3 days)	8 (+/-3 days)	10 (+/-3 days)	12 (+/-3 days)	14 (+/-3 days)	16 (+/-3 days)	18 (+/-3 days)	20 (+/-3 days)	22 (+/-3 days)	24 (+/-3 days)	26 (+/-3 days)	28 (+/-3 days)
Lumateperone dispensation	X	X	X	X	X	X	X	X	X	X	X	X	X	X	X		
Lumateperone return and compliance check		X	X	X	X	X	X	X	X	X	X	X	X	X	X	X	

AE = adverse event; AIMS = Abnormal Involuntary Movement Scale; BARS = Barnes Akathisia Scale; CGI-S = Clinical Global Impression Scale-Severity; C-SSRS = Columbia Suicide Severity Rating Scale; ECG = electrocardiogram; ET = Early Termination; HbA1c = hemoglobin A1c; MADRS = Montgomery-Åsberg Depression Rating Scale; MINI = Mini-International Neuropsychiatric Interview; PK = pharmacokinetic; SAE=Serious Adverse Event; SAS=Simpson Angus Scale.

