6.1 Overall Study Design and Plan

Study ITI-007-503 ("Study 503") is an international, open-label, multicenter, 6-month study to assess the safety and tolerability of lumateperone as adjunctive therapy in patients with MDD. The Study will be performed at approximately 120 study centers. No *de novo* patients will be enrolled.

Patients who have safely completed the lead-in studies may be eligible to participate in this Openlabel Safety Study. Lead-in study completion is defined as a patient who completes the doubleblind treatment period (ie, all scheduled visits up to and including Visit 8) of the lead-in study.

The study will be conducted as follows:

- A **Screening Period** of one day in duration. Potential patients rolling over from the leadin studies will be evaluated for eligibility during the Screening/Baseline Visit (Visit 1/Day 1) which is the same visit as Visit 8/Day 43 of the lead-in study. Patients who meet all eligibility criteria at the Screening/Baseline Visit (Visit 1/Day 1) will be dispensed lumateperone 42 mg to be self-administered each evening without respect to food.
- A **26-week Open-label Treatment Period** during which patients will self-administer lumateperone, to be taken each evening, without respect to food. Background ADT should also continue as previously prescribed, with no change of dose from the lead-in studies. Patients will attend visits on Weeks 1, 2, 3, 4, 6, 8, 10, 12, 14, 16, 18, 20, 22, 24, and 26. The Open-label Treatment Period will last a total of 26 weeks. A patient will be defined as a treatment completer if the patient completes the Open-label Treatment Period (all scheduled visits up to and including Visit 16/Week 26).
- A 2-week Safety Follow-up Period. A Safety Follow-up visit will occur approximately 2 weeks after completion of the Open-label Treatment Period or after the Early Termination (ET) Visit. Any ongoing AEs at the Safety Follow-up Visit must be followed until resolution, until the AE stabilizes, until it is determined to be not clinically significant, or until the patient is lost to follow-up.

Patients who prematurely discontinue should be seen for an ET visit as soon as possible and will also be asked to return to for a Safety Follow-up visit approximately 2 weeks after Visit 16/ET visit.

The maximum per-patient study duration for the Open-label Safety Study will be approximately 28 weeks.

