6.3 Study Population

6.3.1 Inclusion Criteria

In addition to the Inclusion Criteria below, patients will be checked for previous participation in an ITI-007 clinical study and for duplicate enrollment by study site staff through Verified Clinical Trials (VCT).

Each patient entering the Open-label Safety Study must meet all of the following criteria:

- 1. In the opinion of the Investigator, the patient must have safely completed the lead-in study.
- 2. The patient must understand the written informed consent for the Open-label Safety Study, provide signed and witnessed written informed consent.
- 3. The patient is taking his/her ADT as prescribed from the lead-in study.
- 4. The patient must agree to continue using highly effective methods of birth control as specified in the lead-in study through the Safety-Follow-up Period of the Open-label Safety Study, or female patients or female partners of male patients must be of non-childbearing potential.

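### Pregnancy reporting stops on the last-dose date when the final visit is missed, and section 8.2.3 does not say whether the window means conception or detection

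*Protocol*

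**What the plan says.** **Pregnancy (Protocol 8.2.3).** The scope is wide: "Study center personnel must report every pregnancy, including pregnancies in female partners of male study patients, from the time consent was obtained". The duty runs "until the final protocol-defined study visit or last known dose of study drug (if a final visit does not occur"). The section does not say whether the dates refer to when the pregnancy began or when it was found. It also sets a 24-hour notification duty that starts when the site learns of a pregnancy, requires follow-up to the end of the pregnancy, and classes abnormal outcomes as SAEs. None of those three sentences carries an end date.

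**Contraception (Protocol 6.3.1, criterion 4).** "The patient must agree to continue using highly effective methods of birth control as specified in the lead-in study through the Safety-Follow-up Period". Patients or partners who cannot conceive are the stated alternative.

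**SAEs (Protocol 8.2.1.4).** "The Investigator will report all SAEs from the time informed consent was obtained until 30 days after the last known dose date of study drug". Non-serious AEs run to the later of the final visit and one day after the last dose.

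**Potential Hy's Law cases (Protocol 8.2.2).** The section gives two end points, but both allow at least 30 days after the last dose.

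**Final visit.** The synopsis states: "A Safety Follow-up visit will occur on Visit 17/Day 197, approximately 2 weeks after the last dose of open-label lumateperone 42 mg". After early termination, patients "will also be asked to return to for a Safety Follow-up visit approximately 2 weeks after Visit 16/ET visit" (6.1).

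**Testing.** In Table 1-1 the row "Serum/urine pregnancy test" is last marked at Visit 16/ET, and section 8.4.3 lists no test at Visit 17. Unscheduled tests are allowed at any time at the Investigator's discretion.

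**The concern.** A pregnancy is recognised some time after conception. A reporting window that closes on the last-dose date therefore leaves no time to recognise conceptions from the final part of treatment. The clause that does this applies to patients who stop and do not come back, a group section 6.4.1 anticipates by listing loss to follow-up as a reason for discontinuation. Partners of male patients have no scheduled test, so their pregnancies come to light only if someone tells the site.

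When the final visit is missed, pregnancy is the only one of the four reporting windows (AE, SAE, Hy's Law, pregnancy) with no time at all after the last dose. No reason is given.

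Safety is the primary objective, and 8.2.3 itself asks for the outcome in mother and child. A site that takes the cut-off literally need not send the notification that leads to that outcome. The SAP plans no pregnancy table, so the effect is on the completeness of safety reporting rather than on a planned analysis.

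**Working it through.** The plan gives no figure of its own to reproduce. The check is date arithmetic on its windows.

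**Inputs from the protocol.** Visit 16 is Day 183 and Visit 17 is Day 197, each ±3 days (Table 1-1). Treatment lasts 26 × 7 = 182 days. SAE reporting ends 30 days after the last dose.

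**Assumptions.**
- The last-dose day is not stated; Day 182 or 183 is used.
- The final protocol-defined visit is taken to be Visit 17.
- The lag L from conception to detection is taken as 10 to 21 days. The documents give no value.

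**Step 1. How much longer the SAE window is.** Let D be the last-dose day and V the day of Visit 17.
- Visit 17 attended: gap = (D + 30) − V. For D = 182, 212 − 197 = 15 days. For D = 183, 213 − 197 = 16 days.
- With Visit 17 between Day 194 and Day 200, the gap runs from 212 − 200 = 12 to 213 − 194 = 19 days.
- If Visit 16 also moves between Day 180 and Day 186, with the last dose on that day or the day before, it runs from 179 + 30 − 200 = 9 to 186 + 30 − 194 = 22 days.
- Early termination, with the ET visit k days after the last dose and Visit 17 14 days after that: gap = 30 − (k + 14) = 16 − k. This is 16 days at k = 0 and zero at k = 16.
- No final visit: gap = (D + 30) − D = 30 days.

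**Step 2. On-treatment conceptions not yet detectable at the cut-off.** Let E be the day on which reporting ends. A conception on day c becomes detectable on day c + L, so the number of treatment days affected is max(0, L − (E − D)). D = 183 is used here.

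| Case | E − D (days) | L = 10 | L = 21 | Share of 182 days |
|---|---|---|---|---|
| No final visit | 0 | 10 | 21 | 10/182 = 5.5% to 21/182 = 11.5% |
| Visit 17 on Day 197 | 14 | 0 | 7 | 0% to 7/182 = 3.8% |
| Reporting to 30 days after last dose | 30 | 0 | 0 | 0% |

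These are shares of treatment time for a patient treated for the full 26 weeks, not shares of pregnancies. For a patient who stops early, the number of days is the same but the share of a shorter treatment period is larger.

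**Step 3. The two readings of 8.2.3.** If the window dates detection, the days in the table are outside the reporting duty. If it dates conception, an on-treatment conception found later is inside it. The text supports either reading.

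**The case against.** The strongest reply is that 8.2.3 already covers these cases. Reporting every pregnancy from consent until a date can mean every pregnancy that begins in that period. The 24-hour duty starts on learning of a pregnancy and has no end date, and the follow-up sentence applies to any pregnancy in a patient or partner. Abnormal outcomes are SAEs, and 8.2.1.5.2 asks for notification of any SAE after consent. This largely stands. A reader might infer that late-found pregnancies are definitely excluded, but the documents establish only that exclusion is one plain reading. Abnormal outcomes within 30 days of the last dose remain reportable in any case. Later ones depend on how 8.2.3 and 8.2.1.5.2 are read against the 30-day limit in 8.2.1.4.

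Three further points narrow the matter:
- For a patient who attends Visit 17, contraception and pregnancy reporting end together. That mismatch arises only when the visit is missed.
- A reader might infer that SAE reporting always runs 30 days beyond pregnancy reporting. It does not, because the 30 days are counted from the last dose. The full difference applies only when there is no final visit.
- A reader might take 5.5% to 11.5% as the loss for all patients, since the last scheduled test is at Visit 16. That range describes what the Visit 16 test could miss. Reporting stays open to Day 197 for those who attend Visit 17, so the corresponding range for them is 0% to 4%.

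It is also fair to say that pregnancy is not itself an AE or SAE under 8.2.3, so nothing obliges the sponsor to match the SAE window. That makes the alignment a matter of judgement. It does not explain a cut-off with no time after the last dose.

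**Conclusion.** The point holds as a gap in the missed-visit clause and an ambiguity about what the window dates. Read literally, a pregnancy conceived on drug and found after the last dose is not reportable when Visit 17 does not occur. With about 120 centers, sites may read the section differently.

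Without a final visit, the SAE window is longer by 30 days and the exposed period is 10 to 21 treatment days (5.5% to 11.5% of 182). With Visit 17 on schedule, the figures are about 15 to 16 days and about 0 to 7 treatment days (0% to 4%). The treatment-day figures rest on the assumed 10 to 21 day lag and on reading the window as the date of detection. The documents give no pregnancy rate and no rate of missed final visits, so the number of pregnancies affected cannot be estimated. This is an inexpensive improvement to safety capture, not a defect that threatens the study's conclusions.

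**What to change.** In Protocol 8.2.3:
1. End pregnancy reporting, for patients and for partners of male patients, at the later of the final protocol-defined visit and 30 days after the last known dose.
2. State that a pregnancy with estimated conception between consent and the end of Safety Follow-up is reportable whenever the site learns of it. Say which date closes Safety Follow-up for a patient who misses Visit 17, so that the new sentence does not carry over the same gap.

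The first change removes the on-treatment gap over the whole assumed lag, since 30 exceeds 21. The second settles conception against detection. An added pregnancy test at Visit 17 is not needed for either and is not proposed, as it would be an extra procedure.

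The cost is a protocol amendment, which under 6.6 needs IRB/IEC approval and Investigator signatures at about 120 centers, and a few more reports to process. There is also a limit to what it achieves. No contact is scheduled after Visit 17, so late cases still depend on patients telling the site, and patients truly lost to follow-up will not be recovered.
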